#### **4.4 Concomitant Medication**

Concomitant medications will be coded using the WHO Drug Dictionary. The number (and percentage) of subjects taking medications will be tabulated by Anatomical Therapeutic Chemical (ATC) class and preferred term (PT).

The tabulations will include concomitant medications taken from the date of the first dose of study medication (Day 1) until 30 days after the last dose of study medication. Medications that did not end prior to the first dose of study medication will be included in the summary.

Prior medications (those with start date prior to the first dose of study medication) will also be summarized by ATC and PT.

All recorded prior and concomitant medications will be presented in a by-subject listing.

#### **4.5 Analyses of the Primary Endpoint**

The primary endpoint is the change from baseline to 3 months in MS/BS in the cancellous envelope. Paired t-tests will be used to compare the differences in dynamic indices between the two time-points using the Bone-Biopsy Population. If the normality assumption of the efficacy data is not satisfied at the 0.01 significance level with Shapiro–Wilk test and if visual inspection of the data deems it necessary, the Wilcoxon signed-rank test will be used to assess changes from baseline. No adjustments for multiplicity will be made. A two-sided p-value < 0.05 will be considered statistically significant. The actual values and change from baseline values will be summarized with descriptive statistics (number of subjects, mean, SD, median, interquartile range, minimum and maximum) by visit, together with 95% CI for the mean.

#### **4.6 Analyses of Secondary Endpoints**

4.6.1 Change from baseline to 3 months in MS/BS in the endocortical, intracortical, and periosteal envelopes

The same analyses described in Section 4.5 will be used.

4.6.2 Change from baseline to 3 months in MAR in the cancellous, endocortical, intracortical, and periosteal envelopes

The same analyses described in Section 4.5 will be used.

4.6.3 Change from baseline to 3 months in BFR/BS in the cancellous, endocortical, intracortical, and periosteal envelopes

The same analyses described in Section 4.5 will be used.

4.6.4 Structural index (Ct.Po/Ct.Ar) in the intracortical envelope at Month 3

The actual values will be summarized with descriptive statistics (number of subjects, mean, SD, median, interquartile range, minimum and maximum), together with 95% CI for the mean.

4.6.5 Static indices in the relevant bone envelopes (cancellous, endocortical, intracortical, and periosteal) at Month 3

The following study endpoints will be summarized with descriptive statistics (number of subjects, mean, SD, median, interquartile range, minimum and maximum), together with 95% CI for the mean.

- OV/BV
- OS/BS
- O.Th
- W.Th
- ES/BS

4.6.6 Change from baseline to 3 months in special histomorphometric variables in the relevant bone envelopes (cancellous, endocortical, intracortical, and periosteal)

Descriptive statistics (number of subjects, mean, SD, median, interquartile range (Q1, Q3), minimum and maximum) will be provided for the following endpoints.

- RmF/BS
- MF/BS
- oMF/BS

4.6.7 Change in s-PINP and s-CTX from baseline to 1 and 3 months

The actual values, change from baseline values, percentage change from baseline values, geometric mean, geometric mean (SE) of ratio (post-baseline value to baseline value) in s-PINP and s-CTX will be summarized descriptively by visit, together with the 95% CI of the mean, for both the Bone-Biopsy and the Safety populations.

4.6.8 Correlations of tissue-based indices of bone formation and bone resorption with s-PINP and s-CTX

Linear regression analyses will be used to assess the relationships between tissue-based indices of bone formation and bone resorption and changes in bone turnover markers at each visit, including

- Changes in MS/BS in each envelope (cancellous, endocortical, intracortical, and periosteal) at Month 3 to changes in s-PINP at Months 1 and 3
- Changes in BFR/BS in each envelope (cancellous, endocortical, intracortical, and periosteal) at Month 3 to changes in s-PINP at Months 1 and 3
- Changes in intracortical MS/BS at Month 3 to changes in s-CTX at Months 1 and 3,
- Changes in intracortical BFR/BS at Month 3 to changes in s-CTX at Months 1 and 3,
- MS/BS in each envelope (cancellous, endocortical, intracortical, and periosteal) at Month 3 to s-PINP at Months 1 and 3

- BFR/BS in each envelope (cancellous, endocortical, intracortical, and periosteal) at Month 3 to s-PINP at Months 1 and 3
- Intracortical MS/BS at Month 3 to s-CTX at Months 1 and 3
- Intracortical BFR/BS at Month 3 to s-CTX at Months 1 and 3
- ES/BS in each envelope (cancellous, endocortical, intracortical, and periosteal) at Month 3 to s-CTX at Months 1 and 3
- Cortical porosity at Month 3 to s-CTX at Months 1 and 3

The analyses include scatter plots, Spearman's rank correlation coefficient, and slopes of simple regression models, together with corresponding 95% CI of Spearman's correlation coefficient using the Bone-Biopsy population.

## **4.7 Safety Analyses**

All safety analyses will be conducted using the Safety population. Unless otherwise specified, no formal statistical hypothesis testing will be performed for safety endpoints, and the presentations will be based on descriptive summaries.

### **4.7.1 Adverse Events**

Analyses of AEs will be performed for those events that are considered to be treatment-emergent adverse events (TEAEs). A TEAE is defined as any AE that was absent (i.e., had not occurred) prior to the start of study drug and which occurs on or after the date of the first dose of study drug and within 30 days of the last dose of study drug, or any AE that started during the study period(s) prior to the start of study drug and worsened in severity after the start of study drug within 30 days of the last dose of study drug.

In any tabulation of adverse events, a subject contributes only once to the count for a given SOC or PT. For summaries by severity, a subject with multiple occurrences of an AE will be represented under the most severe occurrence. For summaries by relationship to study drug, a subject with multiple occurrences of an AE will be represented under the most related occurrence.

The number (%) of subjects with TEAEs will be summarized by SOC and PT. This analysis will also be performed for the following types of AEs: most common ( $\geq 5\%$ ) TEAEs, severe TEAEs, serious TEAEs (SAEs), TEAEs leading to study drug withdrawal, drug-related TEAEs (with probable or possible relationship to study drug), and AEs that are not treatment-emergent.

The number (%) of subjects with TEAEs will also be summarized by PT in order of decreasing frequency.

The number (%) of subjects with TEAEs by SOC and PT will also be tabulated by maximum severity (mild, moderate, or severe). A similar tabulation will be presented by relationship (related or not related) to study drug.

Subject listings will be provided for all AEs by SOC and PT. Listings will also be produced for AEs with outcome of deaths, severe AEs, SAEs, and AEs leading to study drug withdrawal.

#### 4.7.2 Investigator Assessment of Local Tolerance

For each symptom (redness, swelling, pain, tenderness), descriptive statistics (number of subjects, mean, SD, median, interquartile range, minimum and maximum) will be used to summarize 4-point scale scores (0=None, 1=Mild, 2=Moderate, 3=Severe) by visit and timepoint. The maximum severity of each symptom of local skin reaction per subject will be summarized with the number (%) of subjects in each response category by visit. The maximum severity of each symptom of local skin reaction per subject will also be summarized with the number (%) of subjects in each response category by timepoint (including any post dose timepoint).

In addition, for each symptom, the number (%) of subjects in each response category (none, mild, moderate, and severe) will be provided per visit and timepoint. The maximum severity of symptom scores will be similarly summarized for each response category by visit and by timepoint, respectively.

All local tolerance assessment scores will be presented in a listing.

#### 4.7.3 Laboratory Data

Clinical laboratory values will be provided in standard international (SI) units by the central laboratory.

Summaries of laboratory data using descriptive statistics by study visit will be presented based on the SI units, including absolute results and changes from baseline. This includes serum chemistry, hematology, coagulation, urinalysis, and additional tests. In the event of repeat or unscheduled assessments prior to Day 1, the last non-missing value prior to Day 1 will be used to represent the Screening laboratory assessment. Results from other repeat or unscheduled visits will not be included in this summary.

Shift analyses of laboratory data from baseline to each post-baseline visit will be performed. Results for laboratory data will be presented by category (above normal limit, within normal limit, below normal limit). For shift tables, subjects who are missing either assessment will not be included in the percentage calculation (numerator or denominator). In addition, shift analyses of laboratory data from baseline to the worst post-baseline value will be provided. Results from repeat or unscheduled visits will be included in the shift analyses as applicable.

All laboratory data, including repeated values and results from unscheduled visits, will be presented in data listings, with indication of higher or lower than the associated normal range of each laboratory test.

#### 4.7.4 Vital Signs

Vital signs data will be summarized by visit (and timepoint if applicable). Descriptive statistics will be provided for the observed value and the change from baseline values. Results from repeat or unscheduled visits will not be included in this summary.

All vital signs data will be presented for each subject in a data listing.

Criteria for determining vital signs values that are considered potentially clinically significant (PCS) are listed below:

Vital Sign	Criterion
Body Temperature (°C)	≥ 39.0
Heart Rate (bpm)	> 100 > 130 < 45
Supine Systolic BP (mmHg)	> 155 < 80
Supine Diastolic BP (mmHg)	> 100
Standing Systolic BP (mmHg)	> 155 < 80
Standing Diastolic BP (mmHg)	> 100

The number (and percentage) of subjects who have PCS values after the first dose of study drug, but did not have PCS values at baseline, will be presented. For the calculation of the percentages of subjects, the denominator will be based on the number of subjects who had no PCS values at baseline and had at least one post-baseline assessment for the specific vital sign parameter of interest. The numerator will be based on the number of subjects from the denominator who had at least one PCS value post-baseline for the specific vital sign parameter of interest. All vital signs data, including repeat and unscheduled assessments, will be included in determining the incidence of PCS vital sign values. A listing of subjects with any PCS vital sign values will be provided.

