6.4. Dosing and Administration

Subjects will self-administer a single daily dose of 80 µg of study medication (abaloparatide) during the Treatment Period.

The first self-administration is to occur at the study site under observation. On the days of clinic visits, study medication must be administered in the clinic to accommodate procedures. Study personnel may administer the study medication during clinic visits.

Subjects will be trained by study personnel during the Pretreatment Period how to self-inject study medication with the abaloparatide injection pen. If a subject requires assistance with study medication administration, an individual (eg, a family member) who has been trained by study personnel may provide assistance.

Subjects will also be provided written instructions on how to use the abaloparatide injection pen. Subjects will be instructed by the study site to inspect the contents of their injection pen before each injection. If the cartridge contents are not clear and colorless, or if the contents contain particles, the subjects will be instructed not to use the pen and to contact the study site for further guidance. Injections should be administered at the same time each day. If a dose is missed, the dose should be administered as soon as possible up to 12 hours after the missed injection. Any time thereafter, the dose should be skipped and the drug should be administered at the next scheduled time the following day. All injections are to be given in the periumbilical region of the abdomen, rotating the site of injection each day, and administered at approximately the same time every day. If it is deemed medically necessary by the Investigator for an injection to be administered at a site other than the abdomen, the alternate site of injection is to be recorded and the reason for the change documented in the medical chart and eCRF as a protocol deviation. On the first day of study medication administration, the subject should self-inject while in a sitting or lying position at the study site and remain in that position for approximately 5 minutes. The subject is to remain under observation for a minimum of 60 minutes after the initial injection. A blood pressure measurement will be taken 60 minutes after the injection. Subjects are to be instructed to self-inject at home in a location where they have the ability to sit or lie down.

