### **3.4 Baseline Definitions**

Unless otherwise specified, the baseline value is defined as the last value obtained prior to the first dose of study medication.

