#### 4.7.4.2 Heart Rate

The number (%) of subjects experiencing heart rate increase from pre-dose to post-dose and the number of occurrences per subject will be summarized with various threshold values (ranging from >5 bpm to >40 bpm, with threshold values increasing by 5 bpm). The median, minimum and maximum heart rate increase (in bpm) will be provided per threshold value. The number of

occurrences will be summarized using the median, minimum and maximum values. All heart rate data, including repeat and unscheduled assessments, will be included in determining the increase from pre-dose in this summary.

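### The baseline exclusion in the SAP's PCS vital-sign table works by parameter, not by limit, so some new events in the opposite direction or the higher tier drop out of the count

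*SAP*

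**What the plan says.** SAP Section 4.7.4 sets the PCS limits and then the counting rule.

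- **Limits.** Heart rate: >100, >130 and <45 bpm. Supine systolic BP: >155 and <80 mmHg. Standing systolic BP: the same two. Supine and standing diastolic BP (>100 mmHg) and temperature (≥39.0 °C) have one limit each.
- **Who is reported.** The table gives an n (%), described this way: "subjects who have PCS values after the first dose of study drug, but did not have PCS values at baseline, will be presented".
- **Denominator.** "the denominator will be based on the number of subjects who had no PCS values at baseline and had at least one post-baseline assessment".
- **Numerator.** "The numerator will be based on the number of subjects from the denominator who had at least one PCS value post-baseline".
- **Unit of the rule.** Both of those sentences end "for the specific vital sign parameter of interest". Neither refers to an individual limit or to a direction.
- **Baseline.** Under SAP Section 3.4, "the baseline value is defined as the last value obtained prior to the first dose of study medication".

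The same section also promises an individual listing: "A listing of subjects with any PCS vital sign values will be provided". Scheduled values are summarized descriptively by visit and timepoint. SAP Section 5 (item 2) records the PCS criteria as an addition made in the SAP, so the protocol holds no definition to fall back on.

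**The concern.** A baseline exclusion in a table of this kind is meant to stop a pre-existing abnormality from being counted as new. It does that only if the abnormality excluded is the one being counted. Here three parameters carry limits that are opposite (high and low systolic BP, high and low heart rate) or nested (>130 lies inside >100). High systolic pressure at baseline says nothing about whether a later value below 80 mmHg is new. A heart rate of 104 bpm at baseline does not make 135 bpm old.

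Safety and tolerability is a listed endpoint, and the plan looks for haemodynamic effects after dosing. For the first dose, Protocol Section 6.4 says "A blood pressure measurement will be taken 60 minutes after the injection". Protocol Section 7.3 requires blood pressure and pulse one hour after in-clinic doses, and supine and standing pressures at each treatment-period visit. The PCS table is the only planned count of subjects newly below 80 mmHg, above 130 bpm or below 45 bpm. A rule that leaves out subjects who newly reach those values works against the purpose of the table.

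**Working it through.** The SAP states no figure for this rule, so there is nothing to reproduce. The check applies two rules to the same baseline and post-baseline pairs.

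- **Literal rule:** in the denominator if no limit of the parameter is met at baseline; an event if also in the denominator and any limit of that parameter is met afterwards.
- **Per-criterion rule:** in the denominator for a given limit if that same limit is not met at baseline; an event if that limit is met afterwards.

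The limits come from the table in SAP 4.7.4. The pairs are invented test cases, and each subject is taken to have a post-baseline assessment.

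| Parameter | Baseline → later | Literal rule | Per-criterion rule |
|---|---|---|---|
| Supine SBP | 158 → 75 | not in denominator, not an event | event for <80 |
| Supine SBP | 78 → 160 | not in denominator, not an event | event for >155 |
| Heart rate | 104 → 135 | not in denominator, not an event | event for >130 |
| Heart rate | 104 → 44 | not in denominator, not an event | event for <45 |
| Heart rate | 44 → 105 | not in denominator, not an event | event for >100 |
| Supine SBP | 130 → 75 | event | event for <80 |
| Heart rate | 80 → 135 | event | event for >100 and for >130 |

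The rules agree on the last two rows, where baseline is free of PCS values, and differ on the first five.

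**Direction of the error in the count.** A subject who meets no limit at baseline also does not meet any particular limit at baseline. Every event under the literal rule is therefore an event under the per-criterion rule, but not the reverse. The literal count can only be equal or lower.

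**Direction of the error in the percentage.** Take 25 subjects, the approximate planned enrolment (SAP Section 3.1), none below 80 mmHg at baseline.

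- One subject is above 155 at baseline and is the only one to fall below 80: literal 0/24 = 0%; per criterion 1/25 = 4.0%.
- Five subjects are above 155 at baseline and none of them falls below 80, while one of the other 20 does: literal 1/20 = 5.0%; per criterion 1/25 = 4.0%.

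The percentage can therefore be too low or too high.

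**How far a subject must move to be missed.**

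- Systolic, either direction: more than 155 − 80 = 75 mmHg.
- Heart rate, between the high and low limits: more than 100 − 45 = 55 bpm.
- Heart rate, 101–130 to above 130: from 104, 131 − 104 = 27 bpm is enough; from 130, 1 bpm is enough. This is the easiest route.

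**How many subjects.** The documents give no rate of baseline systolic BP above 155. If it were 5–20% (an assumption), 0.05 × 25 = 1.25 to 0.20 × 25 = 5 subjects would leave that denominator. Those are exclusions, not missed events.

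**Whether another table supplies the count.**

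- SAP 4.7.4.1 counts postural falls. A subject at 75 mmHg both supine and standing has a fall of 0 and is not counted.
- SAP 4.7.4.2 reports "The number (%) of subjects experiencing heart rate increase from pre-dose to post-dose" at thresholds from >5 to >40 bpm. A rise from 104 to 135 is 31 bpm, so if 104 was that visit's pre-dose value she is counted at >5 up to >30. No absolute limit is applied, and a fall to 44 is not covered. SAP 4.7.5 does the same for ECG heart rate.
- SAP 4.7.3 (laboratory shifts by direction) and 4.7.5 (QTcF shifts at 450, 480 and 500 msec separately) concern other data. They do show the SAP keeping direction or cut-off apart where it chooses to.

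**The case against.** The best defence is that the table was meant to be read by criterion. Every heart rate above 130 is also above 100, so a separate >130 limit adds nothing to a single parameter-level count and makes sense only if each limit has its own row. A programmer with one row per limit might naturally exclude only subjects who met that row's limit at baseline. The row layout of the published table also cannot be judged from the extracted text. This is a plausible account of intent, but no sentence applies the exclusion that way. The wording can also be read more broadly: the opening sentence names no parameter, so a baseline PCS value in one vital sign could be taken to remove a subject from every row. The SAP needs to settle it.

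The second defence is that nothing is lost from the report, and much of this stands. The PCS listing has no stated baseline restriction, all vital signs are listed by subject, and scheduled values enter the descriptive summaries with minimum and maximum. A heart rate rise may be counted in 4.7.4.2. Protocol Section 7.3 also asks that clinically significant abnormal vital signs after screening be reported as adverse events. A reader might infer that such events are hidden altogether; the documents do not support that. What is missing is the n (%) of subjects newly meeting the limit.

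Third, numbers are likely to be low. Entry requires good general health, with vital signs part of that assessment (Protocol Section 5.1, criterion 4), and the systolic route needs a swing of more than 75 mmHg. Against that, the entry criteria set no numeric blood pressure limit, and stable antihypertensive treatment is allowed (Protocol Section 5.4), so baseline systolic values above 155 are possible.

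**Conclusion.** The point holds as a defect of the counting rule as written. Because exclusion and numerator are both set by parameter, a subject who meets one heart rate or systolic limit at baseline cannot be counted for a different limit of that parameter. No other planned table gives that count.

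The scope is limited. Only heart rate, supine systolic BP and standing systolic BP are affected. Supine and standing are separate parameters, so exclusion from one does not exclude from the other. Diastolic BP and temperature have single limits and are unaffected on the parameter-level reading. The table is descriptive, and the primary analysis of cancellous MS/BS does not depend on it.

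Two stronger conclusions are tempting and not supported. One is that the reported incidence is necessarily understated: only the event count has a fixed direction. The other is that one to five events would be missed: that range is an assumed number of exclusions, and the documents give no basis for the chance that an excluded subject also has an opposite-direction or higher-tier event. The size is about 4 percentage points per omitted event in a study of about 25, with the number of such events unknown and probably small. The conclusion rests on reading the rule literally; if it was meant per criterion, the same sentence is still needed to say so.

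**What to change.** In SAP Section 4.7.4, replace the denominator and numerator sentences with a rule stated for each PCS criterion separately. The denominator is subjects who did not meet that same criterion at baseline and had at least one post-baseline assessment of that parameter. The numerator is those among them who met it at any post-baseline assessment. Align the opening sentence with this, and present one row per criterion: three for heart rate, two for each systolic position, and one for each remaining parameter. A footnote should say that the >100 and >130 bpm rows are nested, so the heart rate rows must not be added together.

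The limits and the listing stay as they are. The cost is a sentence of SAP text and a minor programming change, with no new data.
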